5.1 Investigational and control treatment

Canakinumab (ACZ885) or matching placebo solution for injection will be provided by Novartis as ready-to-use pre-filled syringes. The sites will receive their first shipment of study treatment only after the first screened patient has been registered in the IVRS/IWRS.

Two strengths and respective corresponding matching placebos will be supplied:

- Canakinumab 50 mg in 0.5 mL solution for injection and one placebo formulation matching to this active drug formulation.
- Canakinumab 150 mg in 1 mL solution for injection and one placebo formulation matching to this active drug formulation.

The study drug will be given as subcutaneous injections at randomization, week 2 (month 0.5), and then quarterly beginning at week 12 (month 3). All injections (double dummy design, two syringes of 1 mL for patients randomized to randomization plan A, one syringe of 1ml and one syringe of 0.5 ml for patients randomized to randomization plan B) will be administered at study sites by trained site staff, facilitating both compliance and long-term follow-up for both safety and efficacy outcomes. Please see [Table 5-1](#) below for planned canakinumab injections at study visits. Study treatment and/or placebo will be given in addition to local standards of care for post-MI patients which may include lipid lowering, anti-hypertensive, beta blockers and anti-platelet therapies and is determined by the responsible treating physician. The sites should make alternative arrangements for those patients likely to miss visits due to travel or other reasons. The minimum time between dosing visits after Visit 3 is 30 days.

Table 5-1 Injection Description

Randomization Plan	Treatment Groups	Injections at all visits excluding Screening, month 0.5 and 1.5 visits	Injections at Visit month 0.5
A	Canakinumab 150 mg sc	1 x canakinumab 150 mg and 1 x matching placebo	2 x placebo matching canakinumab 150 mg
A	Canakinumab 300 mg sc	2 x canakinumab 150 mg	2 x canakinumab 150 mg
A	Placebo	2 x placebo matching canakinumab 150 mg	2 x placebo matching canakinumab 150 mg
B	Canakinumab 50 mg sc	1 x canakinumab 50 mg and 1 x 150 mg matching placebo	1 x placebo matching canakinumab 50 mg 1 x placebo matching canakinumab 150 mg

B	Canakinumab 150 mg sc	1 x canakinumab 150 mg and 1 x 50 mg matching placebo	1 x placebo matching canakinumab 50 mg 1 x placebo matching canakinumab 150 mg

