5.2 Treatment arms

Following protocol Amendment 6 patients will be assigned to one of the following 4 treatment arms in a ratio of 1.4 : 1.3 : 1.3 : 2

- Canakinumab 50 mg s.c. at randomization (month 0), placebo s.c. at week 2 (month 0.5) , 50 mg s.c. at week 12 (month 3) and thereafter 50 mg s.c. quarterly
- Canakinumab 150 mg s.c. at randomization (month 0), placebo s.c. at week 2 (month 0.5), 150 mg s.c. at week 12 (month 3) and thereafter 150 mg s.c. quarterly
- Canakinumab 300 mg s.c. at randomization (month 0), week 2 (month 0.5) , week 12 (month 3) and thereafter 300 mg s.c. quarterly
- Placebo s.c. at randomization (month 0), week 2 (month 0.5) , week 12 (month 3) and thereafter placebo s.c. quarterly

with allocation in a 1.3 : 0.7 : 1 ratio to 300 mg, 150 mg and placebo respectively in randomization plan A and 0.6 : 1.4 : 1 to 150 mg, 50 mg and placebo respectively in randomization plan B. All patients will be equally likely to be assigned to randomization plan A or B. Within each of the two randomization plans patients will have a 2:1 probability of being on active treatment. Prior to protocol amendment 6, patients were assigned in a 1:1:1

ratio to the 300 mg arm, the 150 mg arm or placebo. Across trial parts 1 and 2 this will approximately result in a 1:1:1:1.5 allocation to 300, 150, 50 mg and placebo, respectively. More precisely, given about 743 patients in trial part one and 9257 in trial part 2, the overall patient allocation would be approximately 2253 for both the 300 and 150 mg groups, 2160 for the 50 mg group and 3333 for the placebo group (a 1.01:1.01:0.97:1.5 ratio).

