Analyses will take into account the changes in randomization between trial part 1 and trial part 2 (e.g. by stratifying analyses by trial part) and that patients in trial part 2 were not recruited concurrently with those in trial part 1. This ensure no biases arise e.g. due to differences over time (and thus between the two trial parts) in the recruited patient population or background medical care. Unless otherwise specified, patients randomized to the same treatment arm under randomization plan A or B will be analyzed together. This is not believed to introduce any biases with respect to the assessment of endpoints and the standard of care provided to patients, because patients have an equal 2:1 chance of being on an active treatment group under either randomization plan. Thus, it is not considered necessary to also stratify analyses in this respect.

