## **2.4 Key trial design aspects relevant to trial analysis**

### **Randomization and blinding**

Initially, patients were randomized in a 1:1:1 fashion to 300 mg canakinumab with induction dose, 150 mg without an induction dose or placebo quarterly. Following Health Authority feedback on the doses a lower 50 mg dose arm was added in protocol amendment 6 in order to

examine the dose response of canakinumab in preventing recurrent cardiovascular events, and to determine if a dose lower than 150 mg would have a favorable risk benefit ratio. Following this amendment, randomized allocation to the four trial arms was to be unbalanced in order to optimize power, now that three active arms were compared versus a common control arm.

**Figure 2-3 Patient allocation to treatment arms prior and after protocol amendment 6 including reduced patient numbers following protocol amendment 8**

Protocol amendment 6 introduced 50 mg dose. In protocol amendment 8, the total sample size was changed from 17,200 to 10,000. The allocation to active drug is always 2:1 (in Part I, Part IIA and IIB).

Prior to protocol amendment 6, the following two presentations of canakinumab solution for injection in pre-filled syringes are used in CANTOS:

- Canakinumab 150 mg/1 ml, and
- Placebo matching canakinumab 150 mg/1 ml

In addition, the following pre-filled syringes were available to be used for the purpose of implementing the 50 mg arm following amendment 6:

- Canakinumab 50 mg/0.5 ml, and
- Placebo matching canakinumab 50 mg/0.5 ml.

Canakinumab 50 mg/1 ml pre-filled syringes that fully match 150 mg pre-filled syringes were not available near the time of protocol amendment 6. Thus, in order to evaluate 300 mg, 150 mg and 50 mg versus placebo in a fully blinded fashion, a triple-dummy design with 3 injections per visit would have been required. As feedback from investigators indicated that this would constitute an unacceptable burden to patients we identified the approach shown in [Figure 2-3](#) as the most appropriate solution for introducing the 50 mg dose into the CANTOS trial.

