## 7.2 Statistical models used in multiple safety contexts

Safety data will be summarized across the two trial parts and the two randomization plans in trial part 2, both of which might influence safety reporting as described in [section 2.4](#).

For this purpose hazard ratios versus placebo will be estimated for binary safety outcomes (e.g. at least one occurrence of adverse events) using Cox regression stratified for time since index MI and trial part. Time to event methods have been chosen over relative risk regression or logistic regression to account for differential follow-up. This can be implemented using SAS code similar to the following:

```
proc phreg data=dataset;
  class treatment(ref="Placebo") <time since index MI>
    <trial part>;
  model time*event(0) = treatment / ties=exact risklimits;
  strata <time since index MI > <trial part>;
run;
```

Trial part by treatment interactions will be investigated. For selected events, additional predictive baseline covariates may be added to the model, namely age, sex, race, region and other event specific variables. As summary statistics patients with an event per 100 patient years of follow-up (defined as follow-up to first event or censoring) will be reported.

Rates of multiple occurrences of safety events will be compared between treatment groups for selected safety events of special interest, where such an analysis is of interest. A Negative Binomial regression including terms for treatment, trial part, and log (time at risk) as offset variable will be used. This model was chosen, because the number of recurrent events in a population will follow a negative binomial distribution if there is a distribution of different individual Poisson event rates in the population that follows a gamma distribution ([Glynn et al. 1993](#)) ([Glynn and Buring 1996](#)). While the population distribution may not exactly follow a gamma distribution, the maximum likelihood estimation of the additional dispersion parameter compared to the Poisson distribution from the data allows the negative binomial model approximate the data in this respect and to capture the extent of unexplained heterogeneity in the population. The logarithm of the time at risk is used as an offset (i.e. as a covariate with coefficient 1), because a log link function is used in order to effectively analyze the rate of events per time unit. The following SAS code illustrates the statistical model and methods intended for this analysis:

```

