#### 7.4 Safety topics of interest

This section outlines the currently planned analyses based on the current safety profiling plan. The safety profiling plan is an evolving document outlining the clinical safety plan at any stage of the clinical development of a compound. Thus, due to the length of the trial the analyses based on potential and identified risks may have to be updated according to new information while the trial is ongoing.

In general, analyses for adverse events of special interest based on a list of search criteria stored in the Novartis Clinical REsearch Documentation and Information system (CREDI). For each DMC any analyses to be included in DMC reports will be communicated to the academic independent statistician. Number of affected subjects and percentage will be provided by treatment arm. Risk ratio and 95% confidence interval will be provided for each dose versus placebo. If unbalances occur, time to first occurrence and number of occurrences will be evaluated, if appropriate and not already pre-specified. Dependent on the risk medical history or baseline characteristics may have to be considered further beyond what is prespecified below.

Table 7-4 summarizes the AEs that will be included in any summaries and analyses of AEs of special interest.

Frequency tables will be presented for each AEs of interest as well as the associated MedDRA Preferred Terms. Additionally, Kaplan-Meier plot will be presented for time-to-first event for each AEs of interest unless otherwise specified.

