#### **7.4.10 Injection site reactions**

Events of injection site reactions including including SAEs and those reactions leading to drug discontinuation will be summarized by treatment group and presenting both the frequency and the severity of the events.

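### Injection-site reactions are compared by dose with placebo pooled over two injection set-ups, so any set-up effect would bias the 300 mg and 50 mg comparisons in opposite directions

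*SAP*

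**What the plan says.** **Set-ups.** Protocol 5.1 describes the injections as "two syringes of 1 mL for patients randomized to randomization plan A, one syringe of 1ml and one syringe of 0.5 ml" for plan B. For trial part 1, SAP 2.4 (Randomization and blinding) lists only the 150 mg/1 mL syringe and "Placebo matching canakinumab 150 mg/1 ml". Protocol 5.5.4 gives every patient two injections per visit, so part 1 was also 2 x 1 mL.

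**Allocation.** Protocol 5.2 randomizes part 2 "with allocation in a 1.3 : 0.7 : 1 ratio to 300 mg, 150 mg and placebo respectively in randomization plan A". In plan B the ratio is 0.6 : 1.4 : 1 for 150 mg, 50 mg and placebo. The two plans are equally likely. Part 1 was 1:1:1 for 300 mg, 150 mg and placebo.

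**Analysis.** Protocol 9.1 makes pooling the default: "patients randomized to the same treatment arm under randomization plan A or B will be analyzed together". SAP 7.2 says of trial part and randomization plan, "both of which might influence safety reporting", but its Cox model is stratified only by time since index MI and trial part. Injection-site reactions are a listed topic in SAP Table 7-4. For such topics SAP 7.4 states: "Risk ratio and 95% confidence interval will be provided for each dose versus placebo". SAP 7.4.10 says that these events, including serious ones and "reactions leading to drug discontinuation will be summarized by treatment group", with frequency and severity shown; it does not mention plan.

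**The concern.** Injection set-up is fully confounded with dose at both ends of the dose range. The share of patients on 2 x 1 mL rises from none at 50 mg to all at 300 mg, so a purely local effect of what is injected would look like a dose effect on tolerability.

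The reason given for pooling the plans (Protocol 9.1 and 9.4.2, SAP 2.4 and 6.3.1) is that the chance of active drug is 2:1 in either plan. That argument concerns what investigators and patients can infer, and hence endpoint assessment, care and reporting. It does not cover a physical difference in the injection, and injection-site reaction is the outcome most directly exposed to that difference.

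The plan A v plan B comparisons in SAP 2.4 and 6.3.1 are specified for the primary endpoint. Plan is a model term for platelets and neutrophils (SAP 7.4.4 and 7.4.5) but not here. At stake is how local tolerability is read across doses.

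**Working it through.** **1. Reproduce the allocation (Protocol 5.2: 743 patients in part 1, 9,257 in part 2).**
Part 1 has 743/3 = 247.7 per arm. Each plan in part 2 has 9,257/2 = 4,628.5 patients.

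| Arm | Part 1 (2 x 1 mL) | Plan A (2 x 1 mL) | Plan B (1 + 0.5 mL) | Total | Share on 2 x 1 mL |
|---|---|---|---|---|---|
| 300 mg | 247.7 | 4,628.5 x 1.3/3 = 2,005.7 | 0 | 2,253 | 100% |
| 150 mg | 247.7 | 4,628.5 x 0.7/3 = 1,080.0 | 4,628.5 x 0.6/3 = 925.7 | 2,253 | 58.9% |
| 50 mg | 0 | 0 | 4,628.5 x 1.4/3 = 2,160.0 | 2,160 | 0% |
| Placebo | 247.7 | 4,628.5 x 1/3 = 1,542.8 | 1,542.8 | 3,333 | 53.7% |

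The totals match the protocol's 2,253, 2,253, 2,160 and 3,333.

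**2. Apparent risk ratios with no drug effect.**
Let r be the risk with 1 + 0.5 mL divided by the risk with 2 x 1 mL. This is an assumption, since the documents give no value. An arm with share f on 2 x 1 mL has relative risk f + (1 - f)r. For pooled placebo this is 0.537 + 0.463r.

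| r (assumed) | 50 mg v placebo | 150 mg v placebo | 300 mg v placebo | 300 mg / 50 mg = 1/r |
|---|---|---|---|---|
| 1 | 1.00 | 1.00 | 1.00 | 1.00 |
| 0.9 | 0.94 | 1.01 | 1.05 | 1.11 |
| 0.75 | 0.85 | 1.01 | 1.13 | 1.33 |
| 0.5 | 0.65 | 1.03 | 1.30 | 2.00 |
| 1.33 (reversed) | 1.16 | 0.98 | 0.87 | 0.75 |

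Example for r = 0.75: pooled placebo is 0.537 + 0.463 x 0.75 = 0.884, so 50 mg gives 0.75/0.884 = 0.85 and 300 mg gives 1/0.884 = 1.13. The value 0.75 corresponds to risk proportional to volume, 1.5 mL against 2 mL.

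**3. Does stratifying by trial part help?**
Within part 2, placebo is split 50/50. At r = 0.75 its relative risk is 0.875, giving 0.75/0.875 = 0.86 for 50 mg and 1/0.875 = 1.14 for 300 mg. The bias remains. Only the part 1 stratum is free of it, and that holds 248 of 2,253 (11%) of the 300 mg patients and none of the 50 mg patients.

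**4. Would it be noticed?**
Assume a 2% base risk on 1 + 0.5 mL and r about 0.75. The chance of a nominally significant difference (two-sided 5%) in the false direction is about 11% for 300 mg v placebo, 13% for 50 mg v placebo and 30% for 300 v 50 mg. With base risks from 1% to 5% the last figure runs from 17% to 65%. The base risks are assumptions too.

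**5. Comparing within set-up.**
Each comparison then has the same syringes on both sides, so every null risk ratio is 1.00 whatever r is. For rare events the variance of the log risk ratio is roughly proportional to 1/n(dose) + 1/n(placebo):

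- 300 mg: sqrt[(1/2,253 + 1/1,790.5) / (1/2,253 + 1/3,333)] = 1.16
- 50 mg: sqrt[(1/2,160 + 1/1,542.8) / (1/2,160 + 1/3,333)] = 1.21

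For 300 mg, keeping part 1 and plan A as separate strata costs almost nothing more. The inverse-variance information is 123.8 + 872.0 = 995.8, against 997.7 when they are merged.

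**The case against.** The strongest reply is that the harm is hypothetical. The documents contain no injection-site reaction rate and no evidence that the set-up matters. Both set-ups use two injections per visit, so the number of punctures is equal. At r = 1 there is no bias, and at r = 0.9 the distortion against placebo is about 5%. The direction is also open. Protocol 5.1 gives each strength its own matching placebo formulation, and the active concentrations differ (50 mg in 0.5 mL, 150 mg in 1 mL), so the smaller set-up could be the more irritating one. All of this stands and limits the size of the claim. It does not remove the confounding.

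A second reply is that the plan leaves room to adjust. SAP 7.2 allows event-specific covariates for selected events, SAP 7.4 foresees further evaluation if imbalances occur, and SAP section 1 defers supportive detail to a fuller document. That is fair, but adjustment for plan is not pre-specified for this topic. Follow-up prompted by an observed imbalance would also miss a real trend masked by an opposite set-up effect.

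A third reply is that this is one descriptive safety topic without multiplicity control (SAP 7.1). That is correct and bears on priority.

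A reader might also infer that the matched placebo patients are discarded, or that the 150 mg result is compromised. Neither follows. The placebo patients are pooled rather than dropped, and 150 mg has nearly the same mix as placebo (58.9% v 53.7%), so its null ratio is at most 1.03 even at r = 0.5.

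**Conclusion.** The point holds in conditional form. As planned, the 300 mg and 50 mg comparisons for injection-site reactions mix drug with injection set-up, and trial-part stratification does not separate them. If risk with 1 + 0.5 mL is 0.9, 0.75 or 0.5 of that with 2 x 1 mL, the false 300-to-50 mg ratio is 1.11, 1.33 or 2. If the effect runs the other way, the false trend reverses and could hide a true one. These figures rest on the assumed r and on the planned allocation being achieved.

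The documents do not support the stronger statement that a spurious gradient will occur, because they do not show that a set-up effect exists. The primary and key secondary tests, their alpha and the stopping rules are untouched. The change is worth making because the trial already randomized a placebo group within each set-up.

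**What to change.** In SAP 7.4.10, state that every dose-v-placebo comparison of injection-site reactions is stratified by the three-level randomization plan factor already defined in SAP 6.3.1 (part 1, plan A, plan B). In the SAP 7.2 Cox model this factor replaces trial part in the strata statement. Show the frequency and severity table by plan as well as by treatment. The plan A and plan B placebo columns then give a randomized estimate of the set-up effect itself.

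Part 1 and plan A should not simply be merged into one 2 x 1 mL group. Their allocation ratios differ (1:1:1 v 1.3 : 0.7 : 1) and they were not recruited concurrently, so merging them would be the pooling across trial parts that SAP 2.4 rejects. The three-level factor avoids this.

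The cost is SAP wording, one extra table layout and some precision. The standard error of the log risk ratio for this topic is about 16% larger for 300 mg and 21% larger for 50 mg than with all 3,333 placebo patients. A 300 v 50 mg contrast then becomes indirect, through the arms common to both set-ups, because those doses never share a stratum. No new data are needed.

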#### **7.4.11 Vertigo/dizziness**

Events of vertigo and dizziness will be summarized by treatment group and presenting both the frequency and the severity of the events.

#### **7.4.12 Other safety topics**

The following safety topics will be identified using a list of search criteria in the CRS unless specified otherwise.

- Routine risk of QT prolongation will be evaluated as described in [section 7.3.4](#).
- Increased uric acid levels will be assessed by the laboratory analyses described in [section 7.3.2](#).
- Long term effects on on kidney function will be assessed by the laboratory analyses described in [section 7.3.2](#).
- Interactions with vaccines will be assessed separately by drug interactions.

### **8 Interim analyses**

Interim analyses of efficacy, futility and safety will be carried out during the study. Two interim analyses of efficacy will be performed when about 50% of the target number of primary cardiovascular events have been accumulated and the second one when 75% of the planned number of events are available. Criteria for the interim and final analyses will be determined using a fixed Bonferroni split of the alpha allocated to the interim analyses and to the final analyses in order to protect the overall one-sided familywise type I error rate across

all analyses at 2.5%. The fixed total one-sided alpha allocated to both interim analyses of efficacy combined is 0.05%. Of this 0.01% is allocated to the first efficacy interim analysis and 0.04% allocated to the second efficacy interim analysis. The one-sided significance level for the final analysis is thus 2.45%.

Interim analyses for futility will be conducted simultaneously with the two analyses of efficacy. It should be noted that the efficacy criteria are not modified to “buy back” alpha based upon the presence of futility boundaries; this conservative approach ensures that the familywise type I error rate of the study is protected.

Full details on boundaries and stopping rules will be pre-specified in the Charter of the Data Monitoring Committee (DMC). Timing and number of safety analyses will also be specified in DMC charter.

Protocol amendment 8 introduced an additional early futility analysis to be performed at approximately 30% of the target number of 1400 patients have experienced CEC confirmed MACE. The analysis plan of the early futility was discussed in a separate document. No multiplicity adjustment will be made for the additional early futility analysis, because it will not result in rejecting a null hypothesis for efficacy superiority.

Interim analysis will be performed by an independent academic statistical data analysis center at [REDACTED] external to Novartis, who will not be involved in the trial conduct. The results will be reviewed by the Data Monitoring Committee (DMC).

Investigators, Novartis employees and others who are involved in the conduct of the trial and in the analysis of the final trial results, or who have contact with study centers, will remain blinded to the treatment codes and interim analysis results until all monitoring decisions have been made and the database has been locked for final analysis.

## **DMC**

In CACZ885M2301, a DMC will monitor the trial’s progress, safety and efficacy on a regular basis or per the request of the DMC. Details regarding the reasons for the DMC and the grounds for stopping/continuing trials, as well as the DMC procedures are provided in the DMC charter.

## **9 Sample size and power considerations**

Sample size and power considerations are addressed in section 9.6 and 9.7 of the clinical trial protocol.

### **Appendix 1: Post-stroke functional assessment sub-study**

Full details of the planned analyses for the Stroke Functional Assessment Sub-study, will be specified separately, prior to completion of the first Interim analysis.

In line with the primary objective of the post-stroke functional assessment sub-study to evaluate whether canakinumab arms facilitate functional recovery from stroke, the primary endpoint for this sub-study is the modified Rankin scale assessment 90 days post-stroke.

[REDACTED]

Note that while patients were initially randomly assigned to treatments, the subset of patients experiencing a stroke may represent a biased subset. The impact of the occurrence of fatal strokes in the main study on the results of the sub-study also needs to be considered.

Besides basic summary statistics the main study report will report an intention-to-treat analysis that will rank patients from best to worse as

- alive at trial end and no stroke,
- alive at trial end and stroke with best Rankin scale [REDACTED]
- alive at trial end and stroke with worst Rankin scale [REDACTED]
- dead at trial end

Ranking within these categories will be done with earlier stroke/death being worse than a stroke/death occurring later.

